#### **2.4.3 Safety Analysis**

We will describe and descriptively compare proportions of those with clinical endpoints/adverse events such as hospitalizations, urgent clinic/ER visits, and death between the treatment groups, as using chi-square and Fisher's exact tests for dichotomous outcomes with such a small number of participants is unlikely to reliably demonstrate statistical significance.

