4. Skeletal Muscle Biopsy #1: Participants will lie comfortably in the supine position for biopsy of the vastus lateralis muscle of the non-dominant leg. Biopsy sites will be disinfected with chlorhexidine, lidocaine will then be administered to biopsy site. The physician investigator or study clinician will then make a small incision in the skin and insert a needle into the vastus lateralis to remove approximately 150 mg of muscle. Additional passes of the needle may be necessary for an adequate muscle sample. The wound site will be closed with Steri-strips™ (or a suture if subject is allergic to Steri-strips™) and a sterile pressure bandage.
  - a. Muscle specimens will be immediately processed and stored. Muscle specimens will be divided into portions for specific analyses. Any extra tissue will be stored for future analyses.
  - b. The biopsy wound will be compressed and dressed.
5. Randomization: Subject will be randomized following review of the participant safety status by PI.
6. Pharmacokinetics (pK)
  - a. Nursing staff will measure BP, RR, HR, SpO2, and MetHb to ensure subject is at a steady-state before administering the study drug. Baseline assessments of nitrite/nitrate will be collected. Participants will receive their first dose of study drug (20 mg Nitrite vs. Placebo). Then, the following will be assessed: BP(orthostatic hypotension assessment), HR and MetHb, RR and SpO2 every 15 minutes for the 2 hours post-drug administration period per standard operating procedure. If high MetHb level or if subject is hypotensive or symptomatic, after the study drug is administered, the PI or study clinician will be informed and advise on plan for management.
7. Blood assessments:
  - a. Nitrite/Nitrate Serum Levels and other Research Bloods: baseline (before study drug), 30 minutes, 60 minutes
  - b. Platelet Mitochondrial Respirometry: baseline (before study drug), 30 minutes
  - c. Research Inflammatory Indices: baseline (before study drug)
  - d. Heparinized blood will be immediately centrifuged at bedside to separate plasma and red cells and then flash frozen for future analyses. Total volume of blood drawn for 3 samples will be about 80 ml (about 5.4 tablespoons).
8. Skeletal Muscle Biopsy #2 immediately after the 30-minute blood sample is drawn.
9. A breakfast will be provided after the skeletal muscle biopsy #2.

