## 2.2.2 Study Timetable

Study Phase	Pre-Drug Assessments					Midway Assessment	Post-Drug Assessments			
	Consent Visit	Visit 1	Visit 2	Visit 3	Visit 4		Visit 6	Visit 7	Visit 8	Visit 9
Approximate Time between Study Visits		Same day to +30 days	Visit 1 +1 day to ±14 days	Same day to +7 days	Previous Visit +1 day to ±14 days	6 weeks ±5 days	6 weeks ±5 days	Visit 6 days ±14 days	Same day to +7 days	Previous Visit to ±14days
Approximate Duration of each visit	1-2 hours	3-5 hours	3-4 hours	1-2 hours	3-4 hours	1-2 hours	3-4 hours	3-4 hours	1-2 hours	3-4 hours
Fasting prior to arrival					X	X				X
Consent	X									
Medical History	X									
Physical exam	X	X	X	X **	X	X	X	X	X **	X
Vital Signs	X	X	X	X						
Vital Signs with Methemoglobin					X	X	X	X	X	X
Max CPET*		X					X			
Sub-Max CPET*			X					X		
400-Meter Corridor Walk*#		X				X	X			
Steady-state walk*#			X			X		X		
SPPB			X			X		X		
Handgrip			X			X		X		
Home Actigraph	X	*					X			
Questionnaires	X	X					X			

3 Day Food Record (3DFR)**			X					X		
MRS				X					X	
Randomization					X					
Muscle Biopsies 1 & 2					X					X
Blood Draw Approximate total quantity	20 ml+				83 ml	81 ml	20 mL			81 ml
CBC	X+					X	X			
Complete Metabolic Panel (CMP)	X+						X			
25-hydroxy vitamin d (Vitamin D)	X+						X			
HbA1c	X+						X			
TSH	X+									
Nitrite/Nitrate					X	X				X
Inflammatory Indices					X	X				X
Additional Research Bloods					X	X				X

\*Assessment with NIRS

#Assessment with ActiGraph

+ Blood draw may be collected after signing consent and before randomization, blood draw may not include CMP and/or CBC/d if collected within the last 4 weeks

++ 3 Day Food Record distributed at Visit 1 and Visit 6 and collected from subject at Visit 2 and Visit 7

++ If deemed necessary

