### **2.3.10 Randomization and Blinding:**

We will use the high quality pseudo-random deviate generator in SAS® (SAS Institute, Inc., Cary, North Carolina) to randomize participants to NO or placebo in 1:1 ratio. Because of the moderately large sample size and the resulting opportunity for participant characteristic imbalance between the arms and the threat it would pose to internal validity, we will employ an adaptive randomization scheme to ensure balance by design rather than chance with respect to some key characteristics. Specifically, stratified by study site, we will use a variation of the minimization algorithm that can account for both continuous and categorical variables to ensure balance with respect to gender and walking speed with 80% biased coin probability; and simultaneously guard against heavy sample size imbalance. Such adaptive schemes have been shown to be valid alternatives in trials. Study personnel will call in all prescriptions to the independent research pharmacist at the institutional Investigational Drug Service (See Resources and Environment), who will package all drugs/placebos to be similar in physical appearance. We have successfully employed the same process in other recently completed trials. Therefore, all participants and study personnel (except the study statistician and the dedicated provider of clinical care related to study safety) involved in assessments will be blind to treatment assignment.

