## **2.4 STATISTICAL ANALYSIS**

### **2.4.1 Sample Size Justification**

The principle focus of the proof of mechanism trial is the impact of nitrite on mitochondrial energetics. To detect a significant difference in mitochondrial state 3 respiration in permeabilized fibers (the primary outcome for Aim 1), the planned sample size is 35 per group (a total of 70 participants). Respiration data from a previous multi-site RTC that was co-led by [name], showed a baseline values of  $270.30 \pm 99.80$  pmol/min/mg (mean  $\pm$  standard deviation) for State 3 respiration and a pre- to post-intervention change of  $68.5 \pm 97.61$  pmol/min/mg We conservatively anticipate a dropout rate of approximately 14%. Using published methods implemented in commercial software (PASS 2012®, Number Cruncher Statistical Systems, Kaysville, Utah), with 70 patients and 60 anticipated completers, we will be able to detect statistical significance of a difference as small as 71.80 pmol/min/mg in pre- to post-nitrite change with 80% power in a 2-tailed test at the  $\alpha=0.05$  level. The criterion for a minimally clinically important difference (MCID) has not been authoritatively established for the measure, but the above detectable difference corresponds to a moderate to large effect size ( $d=0.74$ ) by Cohen's criterion. Therefore, the planned sample size affords an appropriate level of statistical sensitivity to address the aims in a mechanistic study with proximal biological outcomes such as ours.

For Aim 3, with the anticipated 30+30 completers, we will be able to detect statistical significance of correlations as small as 0.49 and 0.35, respectively, between changes in mitochondrial energetics and changes in physical activity/function and fatigability with 80% power in two-tailed tests at  $\alpha=0.05$  conducted without and with stratification by treatment group. As such, the planned sample size will afford sufficient statistical sensitivity to detect even moderate associations between mitochondria respiration and clinical endpoints.

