The Sponsor of this study protocol, [name], has previously held an IND for sodium nitrite (IND # 70,411) for cardiovascular applications and currently has an approved IND for the use of sodium nitrite for lung transplant recipients (IND # 111,643). The cardiovascular IND involved the administration of sodium nitrite to 69 normal volunteers in 4 phase I-II clinical trials without observed adverse effects. He has also treated 11 participants with sickle cell disease on this IND without observed adverse effects. The lower doses of nitrite used in these investigational treatment regimens – 60-120 mg daily or 20-40% of the dose (300 mg) used in the emergency treatment of cyanide poisoning—do not produce methemoglobin levels greater than 3% and have not been associated with clinically significant hypotension. There have been no adverse events noted in the 80 treated normal human volunteers and patients with sickle cell disease. In another study by [name] et al., 18 healthy adults received an infusion of sodium nitrite totaling 75 mg (15 minutes each x 2 infusions). This was associated with a 7 mm Hg decrease in mean arterial pressure, a peak methemoglobin of less than 3% and no other significant effects. Note this single dose is 1.9 times the larger single dose (tid) we plan to use in this trial.

In [name] current pilot study, 20 mg tid were used, which were lower or similar to the doses of nitrite cited and used safely in any of the noted studies.

To summarize, we anticipate the following symptoms by organ system and likely frequency of risk:

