#### Cardiovascular

- Common: none
- Frequent: hypotension in older participants on higher nitrite doses
- Rare: flushing, tachycardia, hypotension in healthy controls

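### The safety analysis plans no between-arm estimate for the post-dose blood pressure and methemoglobin readings taken in both arms at Visits 4, 5 and 9

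*Combined protocol and SAP*

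**What the plan says.** Section 2.4.3 (Safety Analysis) is a single sentence. The trial will "describe and descriptively compare proportions of those with clinical endpoints/adverse events such as hospitalizations, urgent clinic/ER visits, and death between the treatment groups". The reason given for staying descriptive is that chi-square and Fisher tests on dichotomous outcomes are unlikely to show significance reliably with so few participants.

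The visit schedule collects much more than events. At Visit 4 (section 2.2.1), BP, heart rate and methemoglobin are measured before the first dose. BP with an orthostatic assessment, heart rate and methemoglobin are then measured "every 15 minutes for the 2 hours post-drug administration period per standard operating procedure". Visits 5 and 9 repeat these assessments by reference to Visit 4. The timetable in section 2.2.2 has a row headed "Vital Signs with Methemoglobin", marked at Visits 4 to 9. Both arms follow the same schedule.

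Section 6.1.1 lists as frequent "hypotension in older participants on higher nitrite doses". It lists methemoglobinemia as rare, and hypotension in healthy controls as rare. It also cites a 75 mg infusion in 18 healthy adults that was "associated with a 7 mm Hg decrease in mean arterial pressure".

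Section 10 uses BP and methemoglobin to manage individual participants, including decisions on unblinding and withdrawal.

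**The concern.** The planned safety comparison rests on yes/no events, the type of outcome on which a trial of 70 people is least informative. Meanwhile the trial takes repeated measurements of the two quantities the drug is expected to move, in randomised arms, and no section defines a summary measure or an arm contrast for them. They are not among the endpoints in the synopsis, the hypotheses in section 1.2 or the Aim 1 to 3 analyses in section 2.4.2.

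Two things are at stake. The trial is described as a foundation for later studies, and an estimate of the BP and methemoglobin effect in people aged 70 or over would be one of its more useful safety results. And if the summary measure, visit and time point are chosen after the data are seen, the reported effect depends on that choice.

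**Working it through.** **The plan's own figure.** Section 2.4.3 states none. The only comparable figure is in section 2.4.1, for the primary outcome: a detectable difference of 71.80 with SD 97.61 and 60 completers. The effect size is d = 71.80/97.61 = 0.736. A two-sample t-test with 30 per arm and two-sided alpha of 0.05 then has 80.0% power. The figure reproduces, and 10 losses out of 70 is the stated dropout of about 14%. So the group sizes to use are 35 per arm at first dose and about 30 per arm at Visit 9.

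**Is the remark about event tests right?** Yes.
- Fisher exact power at 35 per arm, for assumed event rates: 2% vs 10% gives 7%; 5% vs 15% gives 14%; 5% vs 20% gives 33%.
- With 0/35 on placebo, 5/35 on nitrite gives p = 0.054, so 6/35 (p = 0.025) is the smallest significant split.
- Zero events in 35 allows a true rate up to 1 − 0.05^(1/35) = 8.2% (one-sided 95%) or 1 − 0.025^(1/35) = 10.0% (two-sided 95%).

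**How precise would the BP contrast be?** The documents give no SD for BP, so a range is assumed. The 95% CI half-width for a difference of two means is t × SD × √(2/n).
- n = 35: t(0.975, 68) = 1.995 and √(2/35) = 0.2390, so the factor is 0.477.
- n = 30: t(0.975, 58) = 2.002 and √(2/30) = 0.2582, so the factor is 0.517.

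| Assumed SD (mmHg) | Half-width, 35 per arm | Half-width, 30 per arm |
|---|---|---|
| 8 | 3.8 | 4.1 |
| 10 | 4.8 | 5.2 |
| 12 | 5.7 | 6.2 |
| 15 | 7.2 | 7.8 |

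The SD here is the residual SD after baseline adjustment. The degree of freedom spent on the covariate does not change these figures at one decimal.

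**Against what benchmark?** The only BP effect in the documents is the 7 mmHg fall after the infusion. It is a rough guide at best. It is mean arterial pressure, not lowest systolic BP, and it follows 75 mg given intravenously to healthy adults. The trial's capsule is 20 mg, and 75/20 = 3.75. Section 6.1.1 instead calls the infusion 1.9 times the larger planned single dose, and 75/1.9 is about 39 mg. Those statements conflict and must be reconciled.

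**Which visits support a randomised comparison?** At Visit 4 everyone randomised and dosed contributes, but it tests a first dose only. Visits 5 and 9 reflect continued dosing but include only those still on study, and section 10 allows participants with hypotension or raised methemoglobin to be withdrawn. At Visit 5 the steady-state walk is timed around the 30-minute blood draw, inside the 2-hour window, so the lowest BP there is not comparable with Visits 4 and 9.

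**The case against.** The strongest case against has five parts.

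*The gap is partly covered.* The overview in section 2.4.2 promises summaries by arm and time point and of change from baseline. Read plainly, that could include BP and methemoglobin. This stands in part, and a reader who infers that the trial would report nothing on these readings goes too far. But the sentence names no safety variable, no post-dose minimum or peak, and no arm difference with a CI. Summaries at each time point do not give the contrast of extremes. Change in pre-dose values could miss the effect: section 2.3.3 reports that plasma nitrite returned to baseline about 3 to 6 hours after a dose, and the morning dose is held before Visit 9.

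*The event list is open.* A reader might infer that only hospitalizations, urgent visits and death will be analysed, or that the plan declares them beyond comparison. Neither is supported. They are introduced as examples, and the plan says only that significance tests are unlikely to be reliable. Symptomatic hypotension recorded as an adverse event would be counted by arm. However, section 8.1 directs to the adverse event form those events that are clinically important and either unexpected or study-related, so smaller BP falls may never enter those proportions.

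*The risk may be small.* A reader might take methemoglobinemia to be the drug's main risk. The documents list it as rare and report levels no higher than 3% at doses below 75 mg. Likewise, hypotension is called frequent only at higher doses; the documents do not say that label applies to this regimen. Both points stand. They bear on the size of effect to expect, not on whether to estimate it.

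*The readings are used.* They drive individual management, and adverse events go to the monitoring board quarterly. True, but neither use produces a between-arm estimate.

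*Precision is limited.* An effect well below 7 mmHg could be indistinguishable from zero. That also stands, and is why an interval is asked for and not a test.

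**Conclusion.** The concern holds in this form: section 2.4.3 plans a descriptive comparison of event proportions and no between-arm estimate for the post-dose BP and methemoglobin series. No other section supplies one.

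The readings would give a 95% CI half-width of 4.8 to 5.7 mmHg at 35 per arm for an assumed SD of 10 to 12 mmHg, and 5.2 to 6.2 mmHg at 30 per arm. Over assumed SDs of 8 to 15 mmHg the range is 3.8 to 7.8 mmHg across both group sizes. These figures rest on SDs that the documents do not give and on the stated dropout.

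It would be too strong to say that the trial cannot address the BP or methemoglobin effect, or that the later visits answer the question for continued dosing without qualification. Descriptive tables may be produced under section 2.4.2, and Visits 5 and 9 are open to selective withdrawal. Safety is not an aim of this proof-of-mechanism trial and the primary inference is unaffected. The change is still worth making, because it adds a usable safety estimate.

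**What to change.** Add to section 2.4.3:

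- The arm difference with 95% CI, without a significance threshold, for lowest post-dose systolic BP, largest orthostatic fall and peak methemoglobin at Visits 4, 5 and 9. Adjust each for the Visit 4 pre-dose value, since later pre-dose values follow treatment. The Visit 4 text does not say that the pre-dose BP is orthostatic. If it is not, state which pre-dose reading adjusts the orthostatic fall.
- Visit 4, in all randomised and dosed participants, as the main estimate, described as a first-dose effect.
- Visits 5 and 9 reported with the number still on study and the withdrawals for hypotension or methemoglobin by arm, and with a note that the Visit 5 walk falls within the post-dose window.
- By arm, the proportion with dizziness or lightheadedness from the diary cards and, separately, the proportion with symptomatic hypotension measured in clinic. The protocol describes no home BP measurement, so the diary cannot supply the second.

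The cost is a short paragraph and a few more tables from data already collected. No visit, measurement or clinical rule changes.

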#### **2.4.4 Handling Missing Data**

The best approach for handling missing data is prevention. Despite our best efforts, missing data will occur. To minimize missing data, we will use a multi-pronged approach:

1. Adherence to protocol measurement completion by participants. We will compensate participants for participation in trial by assessment.
2. Completion of protocol measurements by staff. We employ an experienced group of research staff, familiar with the measurement protocols described. We utilize a double check system during participant visits to assure all data are collected. We have available back-up systems for most of the outcome assessments, should we experience equipment failure. Staff is cross-trained to allow for planned or inadvertent absences.
3. We will clearly document those with missing data and reasons in the CONSORT diagram and compare those with missing data to complete data with respect to available data. Statistical guidelines for handling missing data recommend methods such as multiple imputation, which consider the uncertainty involved in imputing missing data. Multiple imputation is arguably the best available objective method to analytically account for missing data under the ignorable or missing-at-random (MAR) assumption. Specifically, we will generate  $M=5$  imputed values for each missing value, analyze the 5 datasets as though complete, and finally combine the results appropriately so that they reflect the uncertainty involved in imputation. SAS® MI and MIANALYZE procedures will be used. Other approaches to missing data, including the naïve approaches of ignoring the missing values and last-value-carried-forward (LVCF) will also be considered in sensitivity analyses and robustness of the results to using these approaches will be examined.

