### **2.4.2 Data Analysis**

Overview: All statistical analyses will be performed and overseen by the study statistician [name] (see LOS) using SAS® version 9 (SAS Institute, Inc., Cary, North Carolina). Participant

flow will be summarized using a CONSORT diagram. Data will be summarized by intervention arm and time point as well as baseline to follow-up change using appropriate descriptive statistics. First, the baseline participant characteristics will be compared between the two arms. Any significant differences will be noted and accounted for as additional covariates in the sensitivity analyses. Second, main analyses to address the aims will be performed as outlined below using multiple imputation for missing data. The primary analysis will be performed to test the primary hypotheses H1a about the primary outcome of mitochondrial respiration (high resolution respirometry). Secondary analyses will be performed for remaining hypotheses, secondary outcomes and other exploratory analyses. Third, we describe below our primary approach to missing data and a set of sensitivity analyses by including additional covariates and ignoring missing data.

**Baseline Comparison:** Due to the adaptive randomization scheme, it is unlikely that baseline participant characteristics will be significantly different between the arms. If we do find any, they will be included as additional covariates in the sensitivity analyses. We will not alter the primary analytic strategy to preserve its a priori nature and predictability. We will use independent samples t- or Wilcoxon rank sum tests, as appropriate based on distributional properties, to compare continuous baseline characteristics between the intervention arms. For categorical baseline participant characteristics, we will use chi-square and Fisher's exact tests, as appropriate. Statistical significance of the intervention term will be interpreted as indicating the need to include them as covariates in sensitivity analyses.

**Aim 1 Analysis:** Analysis of covariance (ANCOVA) model using the SAS® GLM procedure with baseline to follow-up change in mitochondrial respiration (high resolution respirometry) as the dependent variable, intervention arm (nitrite/placebo) as the effect of main interest, and the baseline value of mitochondrial bioenergetics as a covariate. The magnitude and statistical significance at  $\alpha=0.05$  of the nitrite vs placebo contrast will serve as the formal test of the primary hypothesis H1a.

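### With only 5 imputations and no stated seed, the primary p-value carries avoidable Monte Carlo noise; the test stays valid, but a larger M is nearly free

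*Combined protocol and SAP*

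**What the plan says.** Section 2.4.2 (Data Analysis) states that the "main analyses to address the aims will be performed as outlined below using multiple imputation for missing data". This covers the single formal test of H1a: an ANCOVA of change in mitochondrial respiration on arm, with the "baseline value of mitochondrial bioenergetics as a covariate", judged at the 0.05 level.

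Section 2.4.4 (Handling Missing Data) sets M=5 and says to "analyze the 5 datasets as though complete" before combining them. It adds that the SAS "MI and MIANALYZE procedures will be used". It gives no seed, no imputation model and no check on Monte Carlo error. The sensitivity analyses in that section change the method (ignoring missing values, last value carried forward). None changes the number of imputations or the seed.

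Section 2.4.1 (Sample Size Justification) plans for 70 randomised and 60 completers.

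**The concern.** Five imputations are usually defended on efficiency: the pooled estimate is nearly as precise as with very many. That describes variance averaged over repeated draws. It does not say how far one reported p-value would move under another seed. This trial rests its primary claim on one test at 0.05, and section 2.4.2 says the primary strategy is to be left unaltered so that it stays a priori and predictable. A p-value that moves materially with an unstated seed works against that aim. Sections 2.3.5 and 2.3.10 also exempt the study statistician from blinding, so it is worth removing any discretion over the seed, whatever the intent. At stake is whether a moderately borderline result would look the same under another, equally legitimate, draw.

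**Working it through.** **Inputs.** From section 2.4.1: 35 per arm randomised, 30 per arm completing, SD of change 97.61 pmol/min/mg, detectable difference 71.80, two-sided 0.05, 80% power. From section 2.4.4: M=5.

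**1. The plan's own figure.** A two-sample t-test (noncentral t) with 30 per arm and SD 97.61 gives a detectable difference of 71.804 and power 0.79996 at 71.80. Effect size: 71.80/97.61 = 0.736. Dropout: 60/(1 - 0.14) = 69.8, so 70, with 10/70 = 14.3% missing. The stated figures reproduce.

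**2. Efficiency.** Relative efficiency is 1/(1 + 0.143/M). At M=5 this is 1/1.0286 = 97.2%. On this criterion M=5 is adequate.

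**3. Size of the Monte Carlo noise by hand.** Suppose the outcome alone is missing, imputation uses arm and baseline, and change is unrelated to baseline. The between-imputation variance B is then roughly the complete-case variance of the arm difference minus the full-data variance:

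- Complete case: 97.61² × 2/30 = 635.2, so SE 25.2.
- Full data: 97.61² × 2/35 = 544.4.
- B ≈ 635.2 - 544.4 = 90.7.

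The seed-to-seed SD of the pooled estimate is √(B/M): √(90.7/5) = 4.3 at M=5, √(90.7/50) = 1.3 at M=50 and √(90.7/100) = 0.95 at M=100. Divided by 25.2, the M=5 value is 0.17 on the t scale, so 95% of seeds lie within about ±0.33. A complete-case p of 0.04 (t = 2.10, 57 df) then spreads over t = 1.77 to 2.43, or p of about 0.018 to 0.082. This is a lower bound on the spread, because with M=5 the standard error is itself unstable (B is estimated on 4 df).

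**4. Simulation for fixed datasets.** 70 participants, 10 outcomes missing (5 per arm), normal-regression imputation on arm and baseline, Rubin's rules with small-sample degrees of freedom. Each of 15 datasets was re-imputed with 250 seeds. Entries are the 95% range of p over seeds and the share of seeds with p<0.05.

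| Complete-case p | M=5 | M=50 | M=100 |
|---|---|---|---|
| 0.05 | 0.021-0.132 (43%) | 0.039-0.068 (42%) | 0.043-0.062 (39%) |
| 0.04 | 0.017-0.112 (59%) | 0.031-0.056 (89%) | 0.034-0.050 (97%) |
| 0.03 | 0.012-0.089 (78%) | 0.023-0.042 (99.8%) | 0.025-0.039 (100%) |
| 0.02 | 0.007-0.069 (92%) | 0.015-0.029 (100%) | 0.017-0.026 (100%) |
| 0.01 | 0.003-0.045 (98%) | 0.007-0.016 (100%) | 0.008-0.014 (100%) |

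Separate runs widen the p=0.04 row only slightly: about 0.016-0.12 at M=5, 0.03-0.056 at M=50 and 0.032-0.051 at M=100.

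Dropout matters. At complete-case p=0.04 and M=5, the range is 0.023-0.080 (71% significant) with 5 of 70 missing, and 0.012-0.137 (55%) with 14 of 70 missing.

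**5. Simulation over whole trials** (3,000 per setting, 10 of 70 missing):

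| True difference | M | Two seeds disagree on p<0.05 | Rejection rate |
|---|---|---|---|
| 0 | 5 | 2.6% | 4.4% |
| 0 | 50 | 0.8% | 5.0% |
| 71.80 | 5 | 8.4% | 77.1% |
| 71.80 | 50 | 2.4% | 79.0% |
| 71.80 | 100 | 1.3% | 79.4% |

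Other runs, one assuming a pre-post correlation of 0.52, put the disagreement at the design effect at about 6-7% for M=5 and 1-2% for M=50.

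**The case against.** The strongest reply is that nothing in the plan is wrong. Rubin's rules allow for finite M, the type I error is intact and the pooled estimate keeps its interpretation. This stands. A reader might infer from the p-value ranges that the primary test is invalid; neither the documents nor the calculations support that.

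A reader might also infer that the same program could give opposite answers on the same data. That is too strong. Once a seed is set, the program returns the same result each time, and section 7.1 says the biostatistics group follows set guidelines for code documentation and reproducibility. Those guidelines do not state a seed for this analysis. Fixing one stops seed selection but leaves the result tied to one arbitrary draw.

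Third, ranges at a complete-case p near 0.05 are chosen on the worst case. Under the plan's figures, p falls between 0.045 and 0.055 in only about 2.5% of trials at the design effect (1% under the null). There a larger M hardly helps: pairs of seeds still disagree about 44% of the time at M=50, against 48% at M=5. This also stands, so the whole-trial figures should lead. The useful gain is at complete-case p of about 0.02 to 0.04.

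Finally, the planned sensitivity analysis that ignores missing values needs no seed, and under these assumptions it is close to what imputation converges to as M grows. An unlucky draw would often show beside it. That helps, but it is a sensitivity result and does not replace the primary p-value.

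**Conclusion.** The point holds as a low-cost improvement to a valid analysis. At M=5, about 6-8% of trials at the design effect and 2-3% under the null would change their verdict at 0.05 with a different seed. At M=50 the figures are about 1-2% and 1%. M=5 also gives up about 1-2 points of power in a design set at 80%. Results with a complete-case p of 0.01 or less are little affected, and no M settles a result lying almost exactly on 0.05.

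These sizes assume 10 of 70 outcomes missing at random, balanced by arm, and an imputation model equal to the ANCOVA, since the plan states none. Less dropout shrinks the effect and more enlarges it; the direction does not change.

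**What to change.** In section 2.4.4, replace M=5 with a larger pre-specified number, such as 100, and state the seed. The documents set no threshold for M; 100 is suggested because at a complete-case p of 0.04 it brings about 97% of seeds to the same side of 0.05, against about 90% at M=50. The cost is trivial computing time at N=70 and a one-line protocol edit. Section 4 requires prospective IRB approval of protocol modifications, so it is simplest to include it in the next amendment.
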